4.1.4 Data imputation

In general, missing data will remain as missing and the missing values will not be adjusted. There are some exceptions described below.

Adverse events

Missing values will be treated as missing except for causality, toxicity, intensity, seriousness and outcome of an AE, in which case a “worst case” approach will be taken. If causality is missing, it will be set to “related”. If intensity is missing, it will be set to “severe”. If seriousness is missing, it will be considered as a Serious Adverse Event (SAE). If outcome is missing and no date is given for the outcome it will set to “not yet recovered”.

Dates for adverse event and concomitant medication

Missing or partial start dates for AEs and concomitant medication data will be handled in the following way:

- If the start date is totally missing, the date will still be missing.
- If the start date is partial where only months and year are given, then the two cases are considered:
 - 1 If the available partial date (month and year) is before the month and year of treatment start date, then the AE/medication will be considered as pre-treatment and the date will be imputed as the start (1st) of the month.
 - 2 If the available partial date does not indicate that the AE/medication has started before the treatment start, then the AE/medication will be considered as treatment emergent/concomitant. The date will be imputed as the start (1st) of the month (if the month is not same as that of the treatment start date) or treatment start date (if the month is same as the treatment start date).
- If the start date is partial where only the year is given, then the two cases are considered:
 - 3 If the available partial date (year) is clearly before the year of treatment start date, then the start date is imputed as start of the year (1st January YYYY).
 - 4 If the available partial date (year) is equal to or after the year of treatment start date, then the start date will be imputed as start of the year (1st January YYYY) (if the year is not same as that of the treatment start date) or treatment start date (if the year is same as the treatment start date).

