4.7.1 Adverse events

Adverse events (AEs) will be classified according to the latest effective version of MedDRA.

A treatment emergent adverse event (TEAE) is any adverse event occurring after the administration of the IMP and within the time of residual drug effect, or a pre-treatment adverse event or pre-existing medical condition that worsens in intensity after administration of the IMP and within the time of residual drug effect.

The time of residual drug effect is the estimated period after the administration of the IMP, where the effect of the product is still considered to be present based on pharmacokinetic, pharmacodynamic or other substance characteristics. The residual drug effect is generally accepted to be 5 times the terminal half-life. The terminal half-life of imlifidase is expected to be within the range of approx. 100 hours, i.e. in this study the residual drug effect is likely to be well within the 29 Day assessments. All AEs occurring up to Day 29 are regarded as treatment emergent.

An AE overview summary table will be prepared including the number of patients reporting an AE, the percentage of patients (%) with an AE, and the number of events (E) reported for the following categories:

- TEAEs
- Related TEAEs (TEAEs considered to be possibly or probably related to IMP as judged by the investigator)
- Related Serious TEAEs
- Deaths
- Treatment-emergent Serious Adverse Events (SAEs)
- TEAEs leading to withdrawal
- Severe and life-threatening AEs

Treatment-emergent AEs will be summarised in a table by dictionary level, i.e., System Organ Class (SOC) and Preferred Term (PT) for MedDRA. The table will display the total number of patients reporting a TEAE, the percentage of patients (%) with a TEAE and the number of events (E) reported. TEAEs will be presented by SOC sorted alphabetically and PT sorted in decreasing frequency of occurrence. For the summary tables the SAF set will be applied.

Summary tables will be prepared for:

- All TEAEs
- TEAEs by causality (related/unrelated)
- TEAEs by intensity
- Related TEAEs by intensity
- SAEs
- SAEs by causality (related/unrelated)
- Treatment-emergent SAEs
- Treatment-emergent SAEs by causality (related/unrelated)

- Treatment-emergent SAEs leading to death
- TEAEs leading to withdrawal

Data listings will be provided for:

- All TEAEs sorted by patient number
- All TEAEs sorted by MedDRA SOC and PT
- SAEs
- Treatment-emergent SAEs
- Treatment-emergent SAEs leading to death

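### SAP 4.1.4 classes month-and-year AE start dates as treatment emergent with no upper limit, against the Day 29 cut-off, and states no class for year-only or missing start dates

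*SAP*

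**What the plan says.** SAP 4.1.4 (Data imputation) handles incomplete AE start dates as follows.

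- **Month and year, before the treatment month (case 1):** pre-treatment, dated to the 1st of the month.
- **Month and year, otherwise (case 2):** "then the AE/medication will be considered as treatment emergent/concomitant". On the date itself: "The date will be imputed as the start (1st) of the month (if the month is not same as that of the treatment start date"); in the treatment month the date becomes the treatment start date.
- **Year only (cases 3 and 4):** a date is imputed. For an earlier year, "then the start date is imputed as start of the year (1st January YYYY"). For the treatment year it is the treatment start date, and for a later year 1 January. Neither case names a class.
- **No date:** "If the start date is totally missing, the date will still be missing".

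On other missing AE items the same section says "Missing values will be treated as missing except for causality, toxicity, intensity, seriousness and outcome of an AE", and those five get a worst-case value. Start date and treatment-emergent status are not among them.

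SAP 4.7.1 (Adverse events) sets the window: "All AEs occurring up to Day 29 are regarded as treatment emergent". Protocol 12.3.13.2 has the same cut-off. Protocol 12.3.13.3 places later events, from visit 8 to visit 11, in a post-treatment emergent class, which SAP section 8 gives its own listing (16.3.1.8). Under protocol 12.3.13, AE summary tables are limited to treatment-emergent events.

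**The concern.** The study has three AE classes: pre-treatment, treatment emergent and post-treatment. The month-and-year rule uses only the first two. It plainly covers months later than the treatment month, because it says how to date them, yet it gives them all the treatment-emergent label. For an event dated to a month well after Day 29, SAP 4.1.4 and SAP 4.7.1 then give different answers.

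The class decides where an event is reported. A late event labelled treatment emergent enters the main AE tables. An event that receives no class may enter none of them. With 10 and 20 patients planned per arm, a single event can be visible in a row of a safety table.

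**Working it through.** **The plan's own cut-off.** SAP 4.7.1 gives "The residual drug effect is generally accepted to be 5 times the terminal half-life" and "The terminal half-life of imlifidase is expected to be within the range of approx. 100 hours". So 5 × 100 h = 500 h, and 500 / 24 = 20.8 days. This lies inside Day 29, so the cut-off agrees with its stated basis. The problem is in the date rules.

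**One worked case.** Count the treatment start as Day 1.

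- Treatment on 10 January 2021: Day 29 is 7 February and Day 180 is 8 July.
- An AE dated only May 2021 is imputed to 1 May, which is Day 112.
- SAP 4.1.4 case 2: treatment emergent. SAP 4.7.1 with protocol 12.3.13.3: post-treatment.
- The remainder of February (Days 30-50, 21 days) shares a month with Day 29, so its imputed date, 1 February, is inside the window and treatment emergent is a reasonable default. From 1 March (Day 51) to Day 180 there are 130 days on which the two rules disagree: 130 / 151 = 86% of Days 30-180 and 130 / 180 = 72% of Days 1-180.

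**All start dates.** The same count was made for every treatment start date over three years (2019-2021), taking calendar months whose 1st falls after Day 29.

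| Quantity | Mean | Range |
|---|---|---|
| Calendar months wholly after Day 29 | 5.0 (of 6.9 touched by Days 1-180) | 4 to 6 |
| Share of Days 1-180 in such months | 76% | 67% to 84% |
| Share of Days 30-180 in such months | 90% | 80% to 100% |

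With the last visit at Day 194 (the +14-day window) the two mean shares are 77% and 91%.

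**Year-only dates.** No class is stated, so the result depends on the imputed date.

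- Treatment year: imputed to Day 1, hence treatment emergent if the imputed date is used. On average 72% of Days 30-180 fall in the treatment year.
- Later year: 1 January may fall after Day 29. Treatment on 10 October 2021 makes 1 January 2022 Day 84, so the imputed date would correctly give post-treatment.

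**No start date.** The AE listings in SAP section 8 are treatment-emergent (16.3.1.1, 16.3.1.2), SAEs (16.3.1.3), treatment-emergent SAEs and two further treatment-emergent subsets (16.3.1.4 to 16.3.1.6), pre-treatment (16.3.1.7) and post-treatment (16.3.1.8). There is no listing of all AEs. An undated non-serious AE meets no stated test for any of these. An undated SAE still enters Tables 14.3.6 and 14.3.7 and Listing 16.3.1.3, which carry no treatment-emergent condition.

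**Effect of one event.** With the planned arms, 1 / 10 = 10 percentage points (PE) and 1 / 20 = 5 points (imlifidase). The incidences count patients, so these are maxima: the percentage moves only if that patient has no other event in the row. Otherwise only the event count changes.

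**The case against.** The strongest answer is that cases 1 and 2 only separate pre-treatment from not pre-treatment, for AEs and medications together, and that a programmer would then test the imputed date against Day 29. That would give the right result, and the post-treatment listing shows that the class is meant to be used. But the text does not say so: case 2 states the final class in the SAP's own term. SAP section 6 relies on code review without double programming, so the wording should settle it.

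Other points stand in part.

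- A reader might infer that every partial date is forced into the treatment-emergent class. The explicit label covers month-and-year dates only.
- A reader might infer that undated events vanish or cannot be classified. What is missing is a rule. Undated SAEs stay in the all-SAE outputs, an AE with missing seriousness is set to serious, protocol 12.3.13 promises that all data are listed by patient, and an end date could show that an event was pre-treatment.
- A reader might count all 151 days after Day 29 (180 − 29) as exposed. Days sharing a month with Day 29 are not in conflict.
- Leaving dates missing follows the section's general default, and the worst-case list does not claim to include dates. A worst-case class for undated events is therefore in keeping with the section's approach to AEs, but nothing in the SAP requires it.
- Labelling late events as treatment emergent over-includes in both arms, which is the cautious direction for safety. That does not help undated events, which may be left out.

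**Conclusion.** The point holds as a conflict between two stated rules plus two gaps. For month-and-year start dates in months wholly after Day 29, SAP 4.1.4 read literally contradicts SAP 4.7.1 and protocol 12.3.13.3. For year-only and totally missing start dates, the SAP states no class.

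The 90% figure is a share of calendar time. It is not a forecast of how many AEs are affected: that depends on how many start dates are incomplete, which the documents do not give, and on when events occur. The 10- and 5-point shifts are ceilings that assume the planned arm sizes. The study is descriptive and the primary endpoint is not touched. This is a minor point, worth correcting because the tables would otherwise depend on an unstated programming choice.

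**What to change.** In SAP 4.1.4:

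1. Impute the start date first, then assign pre-treatment, treatment emergent (up to Day 29) or post-treatment from the imputed date. Treatment emergent is the default only when the reported month or year could include onset between treatment start and Day 29. The dates already imputed under case 2 achieve this, because a month that contains Day 29 is dated to its 1st or to treatment start.
2. Apply the same test to year-only cases 3 and 4 and state the resulting class.
3. Class an AE with a totally missing start date as treatment emergent unless its end date is before treatment.

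Every AE then falls into one of the listings already planned. The cost is a few sentences and a few lines of code, with no new data and no new tables.

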4.2 Patient disposition

The summary table for patient disposition will be presented in the following way:

The number of patients screened, the number of patients in the FAS, PPS, PKS and SAF analysis sets, completers and withdrawals with reason for withdrawal will be summarised with frequency and percentage by treatment.

The patient disposition will also be listed by patient.

The patients screened but not allocated to treatment will be presented with the reason(s) for screening failure in a listing.

4.3 Protocol deviations

Deviations from the protocol, as continuously tracked by investigator and sponsor, will be classified as 'minor' or 'major'. The final classification of the deviations will be done before the database lock.

All protocol deviations will be summarised with frequency and percentage for each category of protocol deviation. The FAS dataset will be applied. The protocol deviations will also be listed by patient.

4.4 Demographics and other baseline characteristics

The following demographic variables will be summarised by treatment: Age, sex, race, height, weight and Body Mass Index (BMI). The table will be made for FAS. The demographics variables will also be listed by patient.

Medical and surgical history and concomitant illness will be summarised by using latest effective version of Medical Dictionary for Regulatory Activities (MedDRA), System Organ Class (SOC) and Preferred Term (PT). The FAS dataset will be used. Medical and surgical history and concomitant illness will also be presented in a list by patient.

Only concomitant medication during the treatment will be tabulated by World Health Organization (WHO) drug version 153E, level 4 (chemical/therapeutic/pharmacological subgroup) and level 5 (Chemical substance). The FAS dataset will be used. Concomitant medication during the treatment and before the start of the treatment will be presented in a list.

Previous kidney transplant history will be presented in a summary table by treatment and listed by patient. The FAS set will be used.

The donor type (living or deceased) will be listed by patient.

4.5 Compliance and exposure

A summary table will be presented for exposure. In the table we will have the total dose and percentage of planned dose. The time point for IVIg and Rituximab will also be included in the table. Compliance and the drug exposure will be presented in a list by patient. The list will show start date of treatment, end date of treatment, number of doses or sessions (as applicable), planned dose and actual dose.

4.6 Efficacy

4.6.1 Primary efficacy analysis

The primary endpoint is the maximum reduction in DSA at any time point during 5 days following start of treatment. No formal statistical hypothesis will be tested for the primary endpoint. The FAS and PPS set will both be used for the primary endpoint. The primary endpoint will be calculated as part of the ADaM programming.

The DSAs are given as levels of mean fluorescence intensity (MFI) and genetic region of interest. These parameters are used to calculate the reduction in DSA for individual patients in the following steps:

- 1) Determine the DSAs having MFI levels larger than or equal to 1000 at baseline for the considered patient. Calculate DSA_0 as the sum of these MFI levels.
- 2) Calculate DSA_t for each patient as the sum of the MFI levels for the time point t , using the DSAs from step 1.
- 3) The reduction (%) is calculated as $100 \times (DSA_0 - DSA_t) / DSA_0$ for each patient and time point. In the formula DSA_t is the total MFI level at time t .
- 4) The time point with maximum reduction within 5 days is found and chosen for each patient.

- 5) The maximum reduction per patient is a single value as the primary endpoint for the patient.

The difference in reduction between the two treatments will be presented with 95% CI in a table. The confidence interval for the difference in the reduction is found by using an Analysis of variance (ANOVA) model with treatment as fixed effect.

The reduction of DSAs calculated per patient will also be presented in a summary table by treatment and visit and presented in a mean plot by treatment and time point. The maximum reduction per patient will be listed by patient.

If the normality assumption is violated, sensitivity analyses using transformations of the primary endpoint will be performed.

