4.2. Inclusion Criteria

1. Signed Informed Consent obtained before any study-related procedures
2. Willingness and ability to comply with the protocol
3. Male and/or female donor kidney recipients age ≥ 18 years at the time of screening
4. Presence of DSA(s)
5. Meet the Banff 2017 criteria for active or chronic active AMR
6. At least 25% rise in serum creatinine compared to last individual value taken prior to the AMR. Patients with delayed graft function and AMR within 10 days after transplant (confirmed by kidney biopsy) can be included regardless of serum creatinine level
7. Women of child-bearing potential willing or able to use at least one highly effective contraceptive method throughout the study. In the context of this study, an effective method is defined as those which result in low failure rate (i.e. less than 1% per year) when used consistently and correctly such as:
 - combined (estrogen and progestogen containing) hormonal contraception associated with inhibition of ovulation
 - oral
 - intravaginal
 - transdermal
 - progestogen-only hormonal contraception associated with inhibition of ovulation
 - oral
 - injectable
 - implantable
 - intrauterine device (IUD)
 - intrauterine hormone-releasing system (IUS)
 - bilateral tubal occlusion
 - vasectomised partner
 - true abstinence: When this is in line with the preferred and usual lifestyle of the subject. [Periodic abstinence (such as calendar, ovulation, symptothermal, post-ovulation methods) and withdrawal are not acceptable methods of contraception]
8. Men willing to use double-barrier contraception from the first day of treatment until at least 2 months after the dose of imlifidase, if not abstinent

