7.1.1. Determination of donor specific antibodies

Samples for determination of DSAs and HLA-antibodies will be analyzed in a single antigen bead assay (HLA-SAB) as well as in functional assay e.g. C1q or C3d assay. These assays allow determination of the mean fluorescence intensity (MFI) of antibodies in subject serum reacting to an array of individual HLA immobilized to beads. Analyses of HLA antibodies, including DSA, will be performed centrally. The date and actual time of collection of each sample will be recorded in the eCRF. DSAs for each patient will be identified by respective site. DSAs collected in standard of care at other timepoints will also be recorded in the eCRF

DSA taken at screening will also be analysed at the local lab at each site, in addition to centrally, for determination of presence of DSA(s) for inclusion.

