12.3. Statistical Analysis of Endpoints

12.3.1. Primary efficacy endpoint

The primary endpoint is the maximum reduction in DSA (MFI sum for relevant DSAs) at any time point during the 5 days following the start of treatment. A subject will have at least one DSA and a DSA is considered relevant if it is at least 1000 MFI pre-dose. The reduction is derived as follows:

- 1) Calculate the reduction (%) in sum of DSAs as $100 \times (DSA_0 - DSA_t) / DSA_0$ for each subject and time point. Only DSAs with a pre-dose MFI of 1000 or more will be included in the calculations
- 2) Find the time point with maximum reduction within 5 days for each subject
- 3) The maximum reduction per subject will give a single value as the primary endpoint for the subject

Where DSA_t is the analysis result in total MFI for relevant DSAs at time t.

Due to the exploratory nature of this study, no formal hypothesis will be tested. The difference in reduction between the two treatments will be presented with 95% CI. Each subject will be given equal weight in the calculation of the treatment difference irrespective of number of DSAs for the subjects.

A summary table showing the proportion of reduction of DSAs calculated per subject will also be presented.

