3.1 Full Analysis Set

FAS will consist of all patients treated with any amount of study medication. Patients will contribute to the analysis ‘as randomized’.

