4.6.2 Secondary efficacy analyses

DSA levels up to 180 days after treatment

DSAs will be measured using SAB-HLA assay and a functional assay e.g. C1q or C3d assay. A summary table for the C1q assay will be generated for the sum of MFI levels for DSAs from step 1 for primary endpoint (see Section 4.6.1) by treatment and time point. MFI levels will be listed per patient and time point. Spaghetti plots will show the DSA level versus time for each patient. A mean plot by treatment and time point will be presented.

A list with all DSA by patient and time point will be presented.

HLA-antibodies levels up to 180 days after treatment

Patient listings of MFI values for all HLAs will be presented.

Kidney function change from baseline

The kidney function will be evaluated by the parameters eGFR, P-creatinine and albumin/creatinine ratio in urine. The laboratory parameters will be summarised as part of the safety data tabulation.

The eGFR will be calculated as a part of ADaM programming, using the Modification of Diet in Renal Disease Study (MDRD) equation (2):

$$\text{eGFR (mL/min/1.73 m}^2\text{)} = 175 \times (\text{Cr})^{-1.154} \times (\text{Age})^{-0.203} \times (0.742 \text{ if female}) \times (1.212 \text{ if African American}),$$

where Cr stands for creatinine value and Age are measured in years from birth to screening visit. This formula assumes that Cr is given in the mg/dL unit.

Proportion of patients with graft loss at day 180

The number of patients with graft loss at day 180 will be handled as a binary variable. Graft loss is defined as permanent return to dialysis for at least 6 weeks, re-transplantation, or transplantectomy. The endpoint is a success if the patients have absence of graft loss at day 180. The proportion of patients, which satisfy the success criterium, will be summarized by treatment and listed by patient. The FAS set will be applied.

Signs of transplant glomerulopathy 180 days post treatment

Possible transplant glomerulopathy 180 days post treatment will be handled as a binary variable. The endpoint is a success if the patients have no possible transplant glomerulopathy 180 days post treatment. The proportion of patients, which satisfy the success criterium, will be tabulated by treatment. A list will also be created by patient. The FAS set will be applied.

Change from baseline in histopathology per Banff Criteria at 29 and 180 days

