14.1.7	Table	Exposure (FAS)
EFFICACY DATA		
14.2.1	Table	Difference in maximum DSA reduction and 95% CI (FAS)
14.2.2	Table	Difference in maximum DSA reduction and 95% CI (PPS)
14.2.3	Table	DSA reduction - by time point (FAS)
14.2.4	Table	DSA reduction - by time point (PPS)
14.2.5	Table	MFI levels for DSA c1q - by time point (FAS)
14.2.6	Table	Proportion of patients with absence of graft loss at day 180 (FAS)
14.2.7	Table	Proportion of patients having no signs of transplant glomerulopathy at day 180 (FAS)
14.2.8	Table	Kidney biopsy (Banff) - Scores - by time point (FAS)
14.2.9	Table	Kidney biopsy (Banff) - Change from baseline (scores) - by time point (FAS)
14.2.10	Table	Kidney biopsy (Banff) - Interpretations - by time point (FAS)
14.2.11	Table	Kidney biopsy (Banff) - Shift table - by time point (FAS)
14.2.12	Table	Kidney biopsy () - Scores - by time point (FAS)
14.2.13	Table	Kidney biopsy () - Change from baseline - by time point (FAS)
14.2.14	Table	Number of sessions of PE and IA for 180 days (FAS)
14.2.15	Table	Total IgG - by time point (FAS)
14.2.16	Table	Proportion of patients having reduction in total IgG - by time point (FAS)
14.2.17	Table	Composition of IgG-fragments (SDS-PAGE) - by time point (FAS)
14.2.18	Table	Proportion of patients having no detectable intact IgG (PKS)
14.2.19	Table	Proportion of patients with resolution of AMR at day 180 (FAS)
14.2.20	Table	Patient survival at day 180 (FAS)
14.2.21	Table	Summary of imlifidase (PK) concentrations - by time point (PKS)
14.2.22	Table	Summary of imlifidase PK parameters (PKS)
DISPLAYS OF ADVERSE EVENTS		
14.3.1	Table	Overview of treatment-emergent AEs (SAF)
14.3.2	Table	Summary of treatment-emergent AEs - by SOC and PT (SAF)
14.3.3	Table	Summary of treatment-emergent AEs - by causality (SAF)

14.3.4	Table	Summary of treatment-emergent AEs - by intensity (SAF)
14.3.5	Table	Summary of related treatment-emergent AEs - by intensity (SAF)
14.3.6	Table	Summary of SAEs (SAF)
14.3.7	Table	Summary of SAEs - by causality (SAF)
14.3.8	Table	Summary of treatment-emergent SAEs (SAF)
14.3.9	Table	Summary of treatment-emergent SAEs - by causality (SAF)
14.3.10	Table	Summary of treatment-emergent SAEs leading to death (SAF)
14.3.11	Table	Summary of treatment-emergent AEs leading to withdrawal (SAF)
DISPLAYS OF SAFETY DATA		
14.4.1	Table	Summary of clinical chemistry variables - by time point (SAF)
14.4.2	Table	Summary of haematology variables - by time point (SAF)

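### Does the primary endpoint need a special rule for a treated patient with no DSA of at least 1000 MFI at baseline?

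*SAP*

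**What the plan says.** Inclusion criterion 4 (Protocol 4.2) asks for DSA to be present and gives no MFI cut-off; none of the exclusion criteria in 4.3 gives one either. Protocol 7.1.1 puts the measurement of HLA antibodies, including DSA, in a central laboratory and adds that "DSA taken at screening will also be analysed at the local lab at each site", the local result being used to decide inclusion.

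The primary endpoint is restricted to stronger antibodies. Protocol 12.3.1 states: "A subject will have at least one DSA and a DSA is considered relevant if it is at least 1000 MFI pre-dose". SAP 4.6.1 implements this. Step 1 is "Determine the DSAs having MFI levels larger than or equal to 1000 at baseline for the considered patient", the baseline total DSA_0 is the sum over that set, and the reduction at time t is 100 × (DSA_0 − DSA_t) / DSA_0. The largest reduction within 5 days is the patient's value, and a one-factor ANOVA gives the treatment difference with its 95% CI.

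On population, SAP 3.1 says: "FAS will consist of all patients treated with any amount of study medication". On gaps in the data, SAP 4.1.4 says: "In general, missing data will remain as missing and the missing values will not be adjusted". SAP 4.6.2 uses the same antibody set again for the C1q summary table, which is made "for the sum of MFI levels for DSAs from step 1 for primary endpoint".

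**The concern.** Eligibility and endpoint use different definitions. A patient can enter on a local finding that DSA is present and then have no DSA reaching 1000 MFI at baseline. Protocol 12.3.1 promises at least one DSA per subject, but not one that meets its own definition of relevant. For such a patient the set in step 1 is empty, DSA_0 and every DSA_t are zero, and the formula is 0/0 at all time points, so there is no maximum to pick.

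The patient has broken no entry criterion, so belongs to the Full Analysis Set and is not removed from the Per Protocol Set on that ground. Table 14.2.1, labelled as a Full Analysis Set table, could then rest on fewer patients than the set contains, with nothing in SAP 4.6.1 to say so. Each missing PE patient is a tenth of that arm, and the study is fully unblinded, so a handling rule chosen late would be unwelcome.

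A second worry is that a DSA below 1000 MFI at baseline that later rises would not appear in the DSA-reduction tables (14.2.3 and 14.2.4) or the C1q table (14.2.5).

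**Working it through.** **1. The plan's own figure.** Protocol 12.4 and SAP 2.2 give an expected 95% CI width of about 8 percentage points for 20 + 10 patients, from SDs of 6% and 4% for IgG reduction in two earlier studies. For a one-factor ANOVA with two arms,

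width = 2 × t(0.975, n1 + n2 − 2) × SD × √(1/n1 + 1/n2).

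With n1 = 20, n2 = 10 and SD = 5, midway between the two quoted values, this is 7.93. The stated figure is reproduced.

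**2. Loss of precision if patients without a qualifying DSA drop out.**

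| Imlifidase + PE | SD 4 | SD 5 | SD 6 |
|---|---|---|---|
| 20 + 10 | 6.35 | 7.93 | 9.52 |
| 19 + 10 | 6.41 | 8.02 | 9.62 |
| 20 + 9 | 6.59 | 8.24 | 9.88 |
| 18 + 9 | 6.73 | 8.41 | 10.09 |
| 20 + 8 | 6.88 | 8.60 | 10.32 |

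Losing one PE patient at SD 5 adds 8.24 − 7.93 = 0.31 points, or 0.31 / 7.93 = 4%. The width is proportional to the SD, so that ratio holds whatever the common SD of DSA reduction proves to be. The SD assumption alone moves the width by 9.52 − 6.35 = 3.17 points, about ten times as much.

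**3. How often it could happen.** The documents give no frequency. For an assumed share p, the chance of at least one such patient among n is 1 − (1 − p)^n.

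| Assumed p | Expected in 30 | At least one in 30 | At least one in 10 (PE) |
|---|---|---|---|
| 1% | 0.3 | 26% | 10% |
| 5% | 1.5 | 79% | 40% |
| 10% | 3.0 | 96% | 65% |

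The event is therefore possible, but these percentages are only as good as the assumed shares.

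**4. What the SAP does with the patient.** The percentage cannot be computed, so the patient has no value. SAP 4.1.4 leaves missing values missing, and its listed exceptions concern adverse-event fields and dates only. A patient without a response does not enter the ANOVA. Nothing in the SAP permits substituting 0 or 100.

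**5. Whether the omission biases the comparison.** Membership of the analysed group depends on baseline MFI, defined in SAP 4.1.2 as the last value before treatment starts. Treatment cannot influence it, so the arms remain randomised groups among patients with at least one qualifying DSA.

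**6. Whether the omission is visible.** SAP 4.1.1 requires the number of patients with each numerical summary. SAP 4.2 reports the size of each analysis set by treatment. SAP 4.6.1 lists the maximum reduction by patient. The number without a primary value in each arm is the analysis-set count minus the number analysed.

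**7. Antibodies below the threshold.** SAP 4.6.2 also plans a listing of all DSAs by patient and time point, MFI listings for all HLA antibodies, individual plots of DSA level over time and a mean plot by treatment. SAP 8 numbers these as Listings 16.2.1.3 and 16.2.1.4 and Figures 15.1.2 to 15.1.32. The text attaches the step 1 set to the C1q summary; it does not say that the DSA-level plots are filtered, nor that they are not.

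**The case for a change.** The best argument for a change is that this patient's MFI values are observed, so the missing-data rule does not plainly apply, and other treatments of 0/0 would matter. Suppose the other nine PE patients average between 50% and 90% reduction (an assumption). Coding the tenth as 0 moves the PE mean by (9 × 50 + 0)/10 − 50 = −5 to (9 × 90 + 0)/10 − 90 = −9 points; coding it as 100 moves it by +5 to +1. Against an interval about 8 points wide these are large shifts, and an open-label study gives no protection against a late choice. A reduced n in the table would also not reveal whether the cause was a lack of qualifying DSAs or lost samples.

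It is true that the SAP has no sentence specific to this case. The shifts, however, come from imputation rules that the SAP does not offer and that conflict with its stance of not adjusting for missing values. The cause of a missing value can be found in the planned listings for 30 patients, and SAP 3 has the analysis sets settled and documented at a data review before database lock.

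A fuller remedy would repeat the analysis and tables on the sum of all DSAs. That corrects no wrong result. The 1000 MFI rule is prespecified and identical in both documents. A patient who is positive locally but near background centrally would have a denominator close to zero, so a single unstable percentage could dominate a ten-patient arm.

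**Conclusion.** The observation is correct: the entry criterion and the endpoint use different definitions, and a patient with no DSA of at least 1000 MFI at baseline would have an undefined primary value. It does not call for a change. Read as written, the SAP leaves that patient without a primary value and outside the ANOVA, which is what a competent analyst would do. No bias is shown, because the omission depends on a pre-treatment value. The precision cost is about 4% of the interval width for one PE patient (7.93 to 8.24 at SD 5), in a descriptive study with no hypothesis test. The count by arm can be recovered from planned outputs, and DSAs below the threshold are still listed.

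This rests on three assumptions: that analysts apply the general missing-data rule and do not invent a value; that the number of affected patients is small, which the documents neither confirm nor exclude; and that the IgG-based SDs are a fair guide to DSA reduction. The relative loss in width does not depend on the last of these. The laboratory manual, the text of the cited Banff criteria and the other four country protocols are not available here, so an MFI cut-off applied in practice at entry cannot be ruled out; one at or above 1000 MFI would make the case rarer.
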